#### **10.4.3 Analysis of the Secondary Endpoint(s)**

Secondary endpoint is patient engagement defined as dDPP utilization, which serves as the key mediator. Patient engagement will be measured using data on logins and lesson completion from the Noom platform, and perceptions of provider involvement. Mean logins and lesson completion are both continuous variables measured at 6 and 12 months from baseline. Patient perceived provider involvement will be measured using a single item survey inspired by validated patient satisfaction instruments and delivered via the NYU patient portal.

We will utilize a linear mixed-effect model or GEE to examine the association of intervention with patient engagement and associations of patient engagement with concurrent or lagged clinical outcomes, with practice as a random effect. If significant associations were found, we will explore the extent to which engagement with the program acts as a mediator. We posit that those who engage more fully with the dDPP may engage in healthy behaviors more than those who are less engaged, which should lead to better weight loss outcomes. Here, we propose using a single mediator causal model approach with bootstrap-derived confidence intervals to measure dDPP effect on weight loss through the specific mechanism of patient engagement.

We will also examine differences in primary outcomes and engagement measures using sex as a biological variable. Techniques used to deal with missing data and potential imbalance between treatment arms will be similar to that in the analysis of primary endpoints.

#### **10.4.4 Safety Analyses**

We will periodically review participant records and report hospitalizations and deaths.

#### **10.4.5 Adherence and Retention Analyses**

Adherence and retention will be assessed using the engagement metrics described above.

CONFIDENTIAL

This material is the property of the NYU School of Medicine and NYU Langone Health. Do not disclose or use except as authorized in writing by the study sponsor Behavioral Intervention Template Version: 11 January 2019

#### **10.4.6 Baseline Descriptive Statistics**

The distribution of baseline demographics and clinical outcomes will be summarized and compared by treatment group. Means and standard deviations will be reported for continuous variables. Counts and percentages will be reported for categorical variables. The comparison of distributions by treatment group will be conducted by the two-sample independent t-test (or its non-parametric counterpart, the Wilcoxon's rank-sum test, as appropriate) for continuous variables and the chi-square test (or the Fisher's exact test, as appropriate) for categorical variables.

#### **10.4.7 Planned Interim Analysis**

No formal interim analyses are planned.

#### **10.4.8 Additional Sub-Group Analyses**

No sub-group analyses are planned.

The primary endpoint of weight loss will be analyzed using a two-sided Type I error rate of 0.05. Other outcomes are considered secondary outcomes and no adjustment is required.

#### **10.4.9 Multiple Comparison/Multiplicity**

We will start with univariate analysis of associations of intervention with each clinical and engagement outcome measured at 6 and 12 months. This enables us to see if effect of intervention clinical and engagement outcomes changes with time. If so, we may consider including interaction terms between intervention and time in GEE. We will also examine potential heterogeneity of intervention effect by participant baseline demographics and clinical measures by running stratified GEE. Other potential analyses of interest could be the analysis of association between changes in engagement and changes in clinical outcomes over time.

#### **10.4.10 Exploratory Analyses**

We will start with univariate analysis of associations of intervention with each clinical and engagement outcome measured at 6 and 12 months. This enables us to see if effect of intervention clinical and engagement outcomes changes with time. If so, we may consider including interaction terms between interventions and time in GEE. We will also examine potential heterogeneity of intervention effect by participant baseline demographics and clinical measures by running stratified GEE. Other potential analyses of interest could be the analysis of association between changes in engagement and changes in clinical outcomes over time.

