### **10.5 Sample Size**

The primary hypothesis is whether weight change among patients affiliated with practices enabled with the dDPP-EHR tool suite is significantly different from weight change in patients using the dDPP in conjunction with usual care. Based on the ~40% increase in dDPP lesson completion (17 vs 12) among patients reporting high levels of provider engagement (post hoc analysis conducted by [name] on her GOALS dDPP), we estimated a range of expected effect sizes from 20-60% in lesson completion in the dDPP-EHR intervention arm (approximately equivalent to completing 2-8 more Noom dDPP lessons). We estimate that this increased lesson completion will translate into at least an additional 2.0 kg of weight loss in the intervention (dDPP-EHR) arm, a conservative estimate considering Noom's dDPP trial observed a 4 kg of weight loss difference (6.6 vs 2.4 kg) with the completion of 6 additional dDPP lessons and GOALS noted a 2.5 kg weight loss difference with 5 additional lessons completed. We estimate the 1 year weight loss will be 4.5 kg and 2.5kg for the dDPP-EHR and dDPP alone approaches, respectively. This is also conservative compared to the 6.2 vs 3.7 kg weight loss difference observed in the post-hoc analysis of GOALS dDPP participants reporting high vs. low provider engagement without any data integration (and the presumed enhanced lesson completion it would facilitate). We also assume a standard deviation of weight loss (at 1 year) of 5 kg based on data from Noom and another GOALS dDPPs. Empirical EHR data indicate that the average annual number of distinct eligible patients is approximately 200 per clinic. The proposed study sample provides 97% power to detect a conservative estimate of 30% increase in Noom dDPP session completion and a 2kg increased 12-month weight loss in the intervention arm if we have 200 patients/arm (a

CONFIDENTIAL

This material is the property of the NYU School of Medicine and NYU Langone Health. Do not disclose or use except as authorized in writing by the study sponsor Behavioral Intervention Template Version: 11 January 2019

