conservative recruitment goal considering our prior experience). The same sample provides 93% power to detect a difference of 1.75 kg between arms. As an additional sensitivity analysis, we also calculated estimated power if only 80% of the anticipated patients/clinic and clinics/arm were collected (i.e., 160 patients/arm). This sample still provides 94% power to detect the expected difference of 2 kg between arms. Therefore, we expect to have adequate statistical power to detect a range of differences between arms (assuming two-sided tests with significance level of alpha = 0.05).

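### Stratified GEE will not estimate or test whether the intervention effect differs between subgroups, and section 10.4.8 says no subgroup analyses are planned

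*Combined protocol and SAP*

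**What the plan says.** Section 10.4.10 (Exploratory Analyses) states: "We will also examine potential heterogeneity of intervention effect by participant baseline demographics and clinical measures by running stratified GEE". Section 10.4.9, headed as the multiplicity section, carries almost the same paragraph. Neither section lists the factors, gives cut-points, or says how results from different strata will be compared. The only interaction either section mentions is with time, and it is optional: "we may consider including interaction terms between interventions and time in GEE".

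Section 10.4.8 states: "No sub-group analyses are planned". The same section contains the multiplicity statement for everything beyond the primary endpoint: "Other outcomes are considered secondary outcomes and no adjustment is required".

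Section 10.4.3 adds: "We will also examine differences in primary outcomes and engagement measures using sex as a biological variable". Section 10.4.1 says much the same. Neither gives a method for the examination by sex.

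**The concern.** The stated aim is to learn whether the intervention effect varies with baseline characteristics. The quantity that answers this is the difference between stratum effects, with its standard error. Stratified fitting produces one effect per stratum and stops there. Each stratum also has less power than the whole trial, so two strata with the same true effect can easily fall on opposite sides of 0.05. With no comparison specified, a reader may take that split as evidence that messaging works in one group and not in another.

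The conflict with 10.4.8 adds to this. Examining effect heterogeneity by baseline demographics and clinical measures is subgroup analysis, whatever it is called. With one section planning it and another denying it, nobody can later establish which subgroup results were pre-specified.

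**Working it through.** **Inputs.** From section 10.5: a difference of "at least an additional 2.0 kg of weight loss in the intervention (dDPP-EHR) arm"; "We also assume a standard deviation of weight loss (at 1 year) of 5 kg"; 200 patients per arm, with 160 as a sensitivity case; "assuming two-sided tests with significance level of alpha = 0.05". From section 10.4.1 and the Protocol Summary: 432 patients randomised 1:2, with 144 in control, hence 432 − 144 = 288 over the two messaging arms. An equal split of these, 144 each, is assumed for pairwise comparisons. Clustering, dropout and covariate adjustment are ignored.

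**Step 1: reproduce the plan's power.** SE = 5·√(1/n₁ + 1/n₂) and power ≈ Φ(δ/SE − 1.96).
- 200 per arm, 2 kg: SE = 0.50, Φ(4.00 − 1.96) = 97.9% (plan: 97%).
- 200 per arm, 1.75 kg: Φ(3.50 − 1.96) = 93.8% (plan: 93%).
- 160 per arm, 2 kg: SE = 0.559, Φ(3.58 − 1.96) = 94.7% (plan: 94%).

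The plan's figures are reproduced to within a percentage point.

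**Step 2: same true effect in two strata.** With stratum powers p₁ and p₂, the chance that exactly one stratum is significant is p₁(1 − p₂) + p₂(1 − p₁).

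Example, 144 v 288 in equal halves (72 v 144 per stratum): SE = 5·√(1/72 + 1/144) = 0.722; power = Φ(2/0.722 − 1.96) = 79.1%; discordance = 2 × 0.791 × 0.209 = 33%.

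Example, 144 v 288 split 70/30: stratum powers are 90.6% and 57.4%; discordance = 0.906 × 0.426 + 0.574 × 0.094 = 44%.

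| Comparison, uniform 2 kg | Equal strata | 70/30 strata |
|---|---|---|
| 200 v 200 | 31.1% | 42.4% |
| 144 v 288 | 33.0% | 44.0% |
| 160 v 160 | 40.7% | 50.0% |
| 144 v 144 | 44.2% | 52.5% |

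**Step 3: vary the true effect, equal strata, same four comparisons.**
- No effect: 2 × 0.05 × 0.95 = 9.5%.
- 1 kg: 35% to 41%.
- 1.5 kg: 49% to 50%.
- 2.5 kg: 11% to 25%.
- 3 kg: 2% to 10%.

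**Step 4: the interaction test on the same data.** In simulation (200,000 replicates per scenario; 0 or 2 kg, equal or 70/30 strata) the interaction test rejected in 5% of trials throughout. Discordance matched the formula, for example 32.9% for 144 v 288 with equal halves at 2 kg. Over k independent unadjusted factors, the chance of at least one false rejection is 1 − 0.95ᵏ: 14.3% for three factors and 18.5% for four.

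**Step 5: what the interaction test can detect.** At 144 v 288 with equal halves, the interaction SE is √2 × 0.722 = 1.02 kg. Power for a 2 kg interaction is Φ(2/1.02 − 1.96), about 50%. For 80% power the interaction must be about (1.96 + 0.84) × 1.02 = 2.9 kg.

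**The case against.** The strongest reply is that this is a gap in specification rather than an invalid method. Section 10.4.2 commits to an estimated effect with a robust 95% confidence interval. If that carries over to the stratified fits, anyone can subtract two stratum estimates and divide by the standard error of the difference. That is true, but it describes the very step the plan leaves out.

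The comparison of 33% with 5% can also be called unlike for unlike: the first is disagreement between two stratum tests when a real effect exists, the second is the type I error of one test. The caution is fair. In both cases, though, the truth is that the strata have the same effect, so both figures are chances of wrongly concluding otherwise if that rule is used.

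Section 10.5 regards 2 kg as conservative, and discordance falls for larger uniform effects. This stands, and the range must be given. Discordance rises, however, if the true effect is somewhat smaller than 2 kg.

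The examination by sex need not mean effect heterogeneity, since its method is not given. This also stands; the conflict with 10.4.8 rests on 10.4.9 and 10.4.10, with the sex analysis as a further ambiguity. The word Additional in the 10.4.8 heading does not remove the conflict, because no other section lists a planned set of subgroups.

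Finally, the interaction test has low power and is not itself protected against multiple factors. Both points stand and belong in the plan.

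**Conclusion.** The point holds in two parts. The planned method yields no measure of whether effects differ between subgroups, and 10.4.8 contradicts 10.4.9 and 10.4.10. Both are visible in the text and need no calculation.

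The size is conditional. At a uniform 2 kg and SD 5 kg, a split in significance occurs in about 31% to 44% of trials per two-level factor with equal strata, depending on the comparison, and more often with unequal strata. It is 9.5% with no effect and 2% to 25% at 2.5 to 3 kg.

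A reader might infer that the trial will report false subgroup differences in a third or more of cases. The documents do not support that. They state no rule that heterogeneity is declared when one stratum is significant and another is not, and the figure depends on the true effect and the stratum sizes. These analyses are labelled exploratory, and neither the primary analysis nor its error rate is touched. The change should be made, but the primary conclusion does not depend on it.

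**What to change.** - In 10.4.10, replace the stratified fits with an intervention-by-subgroup interaction in the full-sample GEE, for a short pre-listed set of factors that includes sex, with any cut-points fixed in advance.
- State whether the two messaging arms are pooled or tested jointly in the interaction.
- Report each interaction estimate with its 95% confidence interval, and show stratum estimates alongside it, not alone.
- Remove the duplicate paragraph from 10.4.9 or make it consistent.
- Change 10.4.8 to say that these are exploratory subgroup analyses without multiplicity adjustment, and state how many factors there are.
- State the limited power from Step 5, and that a non-significant interaction will not be read as showing equal effects.

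The cost is SAP wording only; no new data are needed. The drawback is that the interaction intervals will be wide, and the plan should say so.

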### **10.5 Sample Size**

The primary hypothesis is whether weight change among patients affiliated with practices enabled with the dDPP-EHR tool suite is significantly different from weight change in patients using the dDPP in conjunction with usual care. Based on the ~40% increase in dDPP lesson completion (17 vs 12) among patients reporting high levels of provider engagement (post hoc analysis conducted by [name] on her GOALS dDPP), we estimated a range of expected effect sizes from 20-60% in lesson completion in the dDPP-EHR intervention arm (approximately equivalent to completing 2-8 more Noom dDPP lessons). We estimate that this increased lesson completion will translate into at least an additional 2.0 kg of weight loss in the intervention (dDPP-EHR) arm, a conservative estimate considering Noom's dDPP trial observed a 4 kg of weight loss difference (6.6 vs 2.4 kg) with the completion of 6 additional dDPP lessons and GOALS noted a 2.5 kg weight loss difference with 5 additional lessons completed. We estimate the 1 year weight loss will be 4.5 kg and 2.5kg for the dDPP-EHR and dDPP alone approaches, respectively. This is also conservative compared to the 6.2 vs 3.7 kg weight loss difference observed in the post-hoc analysis of GOALS dDPP participants reporting high vs. low provider engagement without any data integration (and the presumed enhanced lesson completion it would facilitate). We also assume a standard deviation of weight loss (at 1 year) of 5 kg based on data from Noom and another GOALS dDPPs. Empirical EHR data indicate that the average annual number of distinct eligible patients is approximately 200 per clinic. The proposed study sample provides 97% power to detect a conservative estimate of 30% increase in Noom dDPP session completion and a 2kg increased 12-month weight loss in the intervention arm if we have 200 patients/arm (a

CONFIDENTIAL

This material is the property of the NYU School of Medicine and NYU Langone Health. Do not disclose or use except as authorized in writing by the study sponsor Behavioral Intervention Template Version: 11 January 2019

conservative recruitment goal considering our prior experience). The same sample provides 93% power to detect a difference of 1.75 kg between arms. As an additional sensitivity analysis, we also calculated estimated power if only 80% of the anticipated patients/clinic and clinics/arm were collected (i.e., 160 patients/arm). This sample still provides 94% power to detect the expected difference of 2 kg between arms. Therefore, we expect to have adequate statistical power to detect a range of differences between arms (assuming two-sided tests with significance level of alpha = 0.05).

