## **10.4 Description of Statistical Methods**

### **10.4.1 General Approach**

The study trial will utilize a patient-level randomized design, with 1:2 randomization of 432 patients from FGP clinics. Analyses will proceed under the intention-to-treat principle. The distribution of primary and other variables for enrolled patients will be summarized and compared by treatment group. Means and standard deviations will be calculated for continuous variables. Counts and frequencies will be calculated for categorical variables. The comparison of distributions by treatment group will be conducted by the independent two-sample t-test for continuous variables and the Chi-square test for categorical variables. We will use generalized estimating equations (GEE) to compare treatment arms with time as a fixed effect and practice as a random effect, to adjust for clustering of patients within practices; a major advantage of GEE is the sandwich variance estimator that is asymptotically robust to misspecification of the correlation structure. We will also report the intra-cluster correlation and time effect from the fitted model. For the second outcome of 7% weight-loss achievement, we will use a similar GEE model with a logit link function. Missing data frequently occur in pragmatic clinical trials with long follow-up. Standard GEE will be unbiased only if data are missing completely at random, which rarely occurs in practice. Thus, we will apply weighted GEE to accommodate the more realistic missing at random assumption. Due to the large number of clinics, providers, and patients, we expect balance by study arm over patient, provider, and clinic characteristics. In case of imbalance, however, we will investigate propensity score weighting to adjust the observed differences. In addition to estimating the effect of the dDPP on weight loss directly, we will explore the extent to which engagement with the program acts as a mediator. We will examine differences primary

CONFIDENTIAL

This material is the property of the NYU School of Medicine and NYU Langone Health. Do not disclose or use except as authorized in writing by the study sponsor Behavioral Intervention Template Version: 11 January 2019

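### Section 10.5's shortfall scenario does not equal 160 patients per arm: 80% of both named quantities gives 128 per arm and 89% power, not 94%

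*Combined protocol and SAP*

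**What the plan says.** Section 10.5 sizes a comparison of two equal arms. The inputs are:

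- Effect: "We estimate the 1 year weight loss will be 4.5 kg and 2.5kg for the dDPP-EHR and dDPP alone approaches, respectively", a difference of 2 kg.
- Variability: "We also assume a standard deviation of weight loss (at 1 year) of 5 kg".
- Test: "assuming two-sided tests with significance level of alpha = 0.05".
- Base case: "2kg increased 12-month weight loss in the intervention arm if we have 200 patients/arm", with stated power of 97%. The same sample is given 93% power for 1.75 kg.

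The section then adds a sensitivity calculation: "we also calculated estimated power if only 80% of the anticipated patients/clinic and clinics/arm were collected (i.e., 160 patients/arm"). Its result is: "This sample still provides 94% power to detect the expected difference of 2 kg between arms". From these figures the section concludes that power is adequate over a range of differences.

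The same section words its hypothesis at practice level: "weight change among patients affiliated with practices enabled with the dDPP-EHR tool suite". Section 10.4.1, however, says: "The study trial will utilize a patient-level randomized design, with 1:2 randomization of 432 patients from FGP clinics". Section 10.1 also calls the trial randomised at patient level. The Protocol Summary and section 4.1 describe three arms. The Summary assigns 144 of the 432 patients to control but does not state clearly how the rest divide between the two messaging arms.

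**The concern.** The scenario names two separate shortfalls: fewer patients from each clinic, and fewer clinics in each arm. Their product is the number of patients per arm, so two 20% losses compound. The sample size given in the bracket reflects only one. Someone who relies on the words believes that the trial keeps 94% power when both recruitment assumptions fail by a fifth, and the calculation does not show that.

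This matters because it is the only power calculation in section 10.5 for a sample smaller than planned. Section 5.6 expects 432 enrolled patients to yield 432 evaluable ones, so there is no other allowance in the numbers.

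The reference to clinics per arm adds to the difficulty. Where patients are randomised, clinics do not belong to arms, so it is unclear which shortfall was being tested.

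**Working it through.** **Method.** For a difference Δ, common SD σ and arm sizes n₁ and n₂, two-sided α = 0.05:

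power ≈ Φ( Δ / [σ √(1/n₁ + 1/n₂)] − 1.960 )

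Each result was also computed with the exact noncentral t distribution. The inputs are those of section 10.5: σ = 5 kg, and Δ = 2 kg or 1.75 kg.

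**Step 1: reproduce the plan's figures.**

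- 200 per arm, 2 kg: 2 / (5 × √(2/200)) = 4.00; Φ(4.00 − 1.96) = 97.9% (t: 97.9%). Stated: 97%.
- 200 per arm, 1.75 kg: 3.50; Φ(1.54) = 93.8% (t: 93.7%). Stated: 93%.
- 160 per arm, 2 kg: 2 / (5 × √(2/160)) = 3.578; Φ(1.618) = 94.7% (t: 94.6%). Stated: 94%.

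All three agree to within one point, so the formula and inputs are those of the plan.

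**Step 2: translate the scenario into patients.**

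Patients per arm = (patients per clinic) × (clinics per arm).

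- Both factors at 80%: 0.8 × 0.8 = 0.64, and 0.64 × 200 = 128 per arm.
- One factor, or the total, at 80%: 0.8 × 200 = 160 per arm.

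This does not depend on the number of clinics, which the documents do not give.

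**Step 3: power at 128 per arm.**

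- 2 kg: 2 / (5 × √(2/128)) = 2 / 0.625 = 3.20; Φ(1.24) = 89.2% (t: 89.0%).
- 1.75 kg: 1.75 / 0.625 = 2.80; Φ(0.84) = 80.0% (t: 79.7%).

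A one-sided test at 128 per arm would give 94.0%, but this does not rescue the sentence. Section 10.5 specifies two-sided tests, and a one-sided calculation at 200 per arm gives 99.1%, not the stated 97%.

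**Step 4: the same question on the planned 432 patients.**

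Assumption: 144 per arm in all three arms (the documents give 144 only for control). At 80% yield, 0.8 × 144 = 115.2, taken as 115, and the pooled messaging arms have 230.

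| Contrast, 2 kg | All patients | 80% yield |
|---|---|---|
| One messaging arm v control | 144 v 144: 92.4% (t: 92.3%) | 115 v 115: 85.8% (t: 85.6%) |
| Both messaging arms pooled v control | 288 v 144: 97.5% (t: 97.4%) | 230 v 115: 93.9% (t: 93.7%) |

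**The case against.** The best defence is that the sentence states its operative sample size, and that 94% is correct for it. Since 160 is exactly 80% of 200, the authors may well have meant one overall 20% loss and described it loosely. This stands as an account of intent, and the documents cannot settle the matter. It does not remove the mismatch: either the words or the numbers must change.

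Several stronger readings are tempting, and the documents do not support them.

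- **The 94% is a miscalculation.** It is not. The error lies between the scenario and the sample size.
- **A clustering allowance is missing.** Sections 10.1 and 10.4.1 randomise patients, so the practice-level wording does not by itself call for a design effect. Nor does 10.4.1 say that randomisation is within, or stratified by, clinic. On its own, the clinic wording is an editorial matter.
- **Power falls much further, for example to 77% at 92 per arm.** That figure applies the 64% yield to 144 per arm. It brings in a separate issue, two-arm sizing for a three-arm trial, and rests on an assumed split. On the pooled contrast, an 80% yield of the planned sample gives about 94%, essentially the stated figure.
- **This sentence is the plan's only protection against lost data.** It is the only power calculation for a shortfall. Section 10.4.2 separately provides outreach to patients with missing data, EHR extraction and weighted GEE.

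**Conclusion.** The point holds in a limited form. As worded, the scenario implies 128 per arm and 89% power for 2 kg. As numbered, 160 per arm and 94% describe a single 20% shortfall in total patients. The gap is 94.6 − 89.0 = 5.6 points when both are computed exactly, or about 5 points from the stated 94%.

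This rests on the plan's own effect, SD and test, and on reading the scenario as reductions in both named quantities. No assumption about attrition or clustering is needed.

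A reader might infer that the trial is underpowered. It is not on this evidence: 89% still supports the section's conclusion for 2 kg. The margin is thinner at 1.75 kg, where 128 per arm gives about 80%, but the plan makes no claim for 1.75 kg at the reduced size.

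**What to change.** Choose one scenario in section 10.5 and make the words and numbers agree:

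1. an overall 80% yield of patients, 160 per arm and 94%; or
2. both reductions, 128 per arm and 89%.

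In either case, remove the reference to clinics per arm, and bring the practice-level wording of the hypothesis into line with patient randomisation.

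Preferably, restate the sensitivity calculation on the planned 432 patients, confirm the split between the messaging arms, and name the contrast. With 144 per arm and an 80% yield, the figures for 2 kg are about 86% for one messaging arm against control (115 v 115) and about 94% for both pooled against control (230 v 115).

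The cost is a change of text. Recruitment, procedures and analysis are unaffected. Under option 2, or for a single-arm contrast, the plan reports a somewhat less favourable figure.
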